NH Resident Data will be collected for consented NH residents from Brief interview of family/friends (see attachment), NH staff interview of the resident (see attachment), NH staff ratings (clinical global assessments of change in overall sleep quality and sleep-related conditions - see Appendix; NH staff sleep reports - see attachment); through primary data collection (actigraph/Fitbit measurements; these are wristwatch-sized devices worn on the wrist); through medical records (age, diagnoses, medical history, and medications); and through NH secondary data from the Minimum Data Set (MDS; all Medicare-reimbursed NHs are required to collect MDS assessments on all residents; the MDS contains information on resident medical conditions, functioning, cognition, psychotropic and pain/analgesic medication use, activities of daily living decline, and sleep-, mood-, and activity-related items). Table 1 summarizes the primary and secondary outcomes and data sources.

NH Staff Data: staff interview data will be collected via audiorecorded qualitative interview (see Appendix).

Data Collection Procedures:

NH Resident Primary Research Data Collection: will consist only of actigraph/fitbit data.

We will measure total sleep time (TST) with data from Micro-Mini Motionlogger Actigraphs (Ambulatory Monitoring Inc., Ardsley, NY).[87] We will define nighttime as 10pm to 6am and will compute TST as the total number of minutes asleep during a nighttime period. We will measure sleep for 7 days at each measurement period (see Figure 2) to obtain reliable measurements and will use the average TST across this period. We will also examine the following: wake after sleep onset (total number of minutes awake during nighttime), how often the resident awoke during the nighttime, sleep efficiency (the ratio of

minutes asleep to minutes awake over the period), and sleep fragmentation (an index of restlessness computed as the percentage of one-minute epochs scored as awake). Sensitivity of actigraph measurement for sleep is very good (actigraphy = sleep when polysomnography = sleep was 0.97). [88]

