For residents with likely mild ADRD (BIMS score above 10) but no lar, the nursing home leadership team and study staff will go directly to the resident to invite their participation and screen their capacity to consent using the same process described above.

All above procedures apply to securing consent for the research study team to have access to NH resident personally identifiable data.

NOTE: the LOCK sleep program does not include any activities that are outside of standard NH practice, therefore NH staff will be free to enroll any NH residents that they believe will benefit into the LOCK sleep program regardless of resident consent status; however the NH leadership team will only be allowed to share with the research study team data for residents who are consented for the study.

- 3. It should be recognized that decision-making capacity may fluctuate, requiring ongoing Y assessment during the course of the research. Is it reasonable to expect that during the course of the research, subjects may lose their capacity to consent or their ability to withdraw?
 - a) Describe what provisions are in place for periodic re-consent. Include the rationale and procedure, the proposed interval, any changes in behavior that might signal the need to re-consent whether or not the proposed interval has elapsed, and any consultative resources that are available for these decisions. Describe the process for re-consent or re-assent, or reassessment of willingness to continue participation.

Re-consenting provisions will not be included because the course of the study is a relatively short 22 weeks (5.5 months), an amount of time in which it is unlikely, although possible, that cognitive capacity will significantly change. Further, the main focus of the intervention is with staff behavior. Staff will be implementing interventions that are considered good standard clinical practice, such as providing meaningful activities during the day to help reduce resident daytime napping and reducing noise and resident interruptions at night to promote uninterrupted sleep. Therefore, is is unlikely, although possible, that resident willingness to continue participation will change over this relatively short amount of time.

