 Use of investigational devices. Please include the clinical adverse events (AEs) associated with each of the devices with an indication of frequency, severity and reversibility. This information can often be found in the Investigator(s) brochure. NOTE: Include any likely adverse effects associated with procedures that participants may experience while in the study.

No investigational devices will be used.

- 3. Use of FDA approved drugs, reagents, chemicals, or biologic products. Please include the clinical adverse events (AEs) associated with each of the drugs with an indication of frequency, severity and reversibility. This information can often be found in the package insert provided by the manufacturer. NOTE: Include any likely adverse effects associated with placebos or washout periods that participants may experience while in the study. N/A
- 4. Use of FDA approved devices. Please include the clinical adverse events (AEs) associated with each of the devices with an indication of frequency, severity and reversibility. This information can often be found in the Investigator(s) brochure. NOTE: Include any likely adverse effects associated with procedures that participants may

experience while in the study.

N/A

5. Describe any risks related to performing study procedures. Please include all investigational, non-investigational, and non-invasive procedures (e.g., surgery, blood draws, treadmill tests).

No more than minimal risk.

Regarding psychological risks to NH residents, the LOCK sleep program including frontline huddling provides a sequence of steps for the process of assessing and responding to sleep problems. During the intervention period NH residents enrolled in the LOCK sleep program will receive actigraph and Fitbit assessment, and although our teams' experience with use of these devices in hundreds of people with dementia indicates that they are widely tolerated as comfortable, there is a small risk a resident may find the devices to be uncomfortable or otherwise distressing. As part of their intervention training, staff will be instructed on behavioral signs of distress. If a participant exhibits significant behavioral distress due to assessment, staff will be instructed on modifications and alternatives. If the distress does not subside, staff will be instructed to discontinue the assessment.

- Describe any risks related to the use of radioisotopes/radiation-producing machines (e.g., X-rays, CT scans, fluoroscopy).
 N/A

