Anticipated AEs related to the intervention: Intervention-related AEs for NH residents might include: a) actigraph/fitbit-related skin reactions such as redness, itching, or other skin conditions or discomfort; b) distress or discomfort associated with actigraph/fitbit-related wear or NH staff attention; c) distress or discomfort associated with other LOCK sleep intervention NH staff attention or requests. Intervention-related AEs for NH staff might include: distress related to interview questions. Such events may be reportable depending upon the seriousness of the event and increase of risk to participant. The NH's treating clinical team's opinion of the seriousness of the event will be solicited and the PI, co-investigator nurse scientist [name] and study co-investigator geriatrician [name] will be consulted to determine seriousness and reportability of the event.

Unanticipated AEs and unanticipated problems related to the intervention: As with intervention-related AEs, unanticipated AEs and unanticipated problems will be evaluated for seriousness with input from the NH's treating clinical team (if applicable), the PI and clinical study team members Drs. [name] and [name] (if applicable) or data-related study team members including data coordinating center leader and study statistician [name] (if applicable).

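### As written, entry into LOCK needs no consent yet brings the actigraph and Fitbit with it, which contradicts the rule that device data are collected only for consented residents

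*Combined protocol and SAP*

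**What the plan says.** **Entry into LOCK.** The note closing Section 7(n) (Research with cognitively impaired persons), Section 2 item 2, says "NH staff will be free to enroll any NH residents that they believe will benefit into the LOCK sleep program regardless of resident consent status". The reason given is that LOCK contains nothing beyond standard nursing home practice. The same rule appears in the Data and Safety Monitoring Plan (DSMP), 1.3.a, and in Section 12, item 1. The limit attached to it in Section 7(n) is that "the NH leadership team will only be allowed to share with the research study team data for residents who are consented for the study"; the other two places have an equivalent clause. The scope of the consent process is described this way: "All above procedures apply to securing consent for the research study team to have access to NH resident personally identifiable data".

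**Devices.** Section 8(a) item 5 and DSMP 1.1 both state: "During the intervention period NH residents enrolled in the LOCK sleep program will receive actigraph and Fitbit assessment". Item d of the resident data flow, in DSMP 1.3.b and again in Section 10(c), has staff identify residents to enter into LOCK and, in the same sentence, collect assessment data for enrolled residents. It does not say whether that means enrolled in LOCK or in the study.

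**Status of the devices.** Section 3(b), Data Collection Procedures: "NH Resident Primary Research Data Collection: will consist only of actigraph/fitbit data". DSMP 1.2 lists among anticipated intervention-related adverse events "actigraph/fitbit-related skin reactions such as redness, itching, or other skin conditions or discomfort", and also distress from wearing the devices.

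**Text pointing the other way.** Section 3(b), Sources of Research Data: "NH Resident Data will be collected for consented NH residents", followed by a list that includes actigraph and Fitbit measurements. Section 10(c), Sources of Materials, says much the same.

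**The concern.** The argument for entering residents into LOCK without consent is that LOCK is ordinary care. That argument cannot cover the actigraph and Fitbit if they are research measurements with their own listed adverse effects. If device wear follows from LOCK entry, the consent exemption for the program carries over to the devices.

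The residents this could reach include those whose legally authorized representative opted out or never responded, and a resident with capacity who declined the study. All of them remain eligible for LOCK under the note. Section 7(n) expects most residents to lack capacity to consent.

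The wording also matters in practice. Section 3(b) says research staff will not enter the homes, so nursing home staff decide day to day who wears a device. The risk section and the DSMP are texts on which an ethics committee or monitoring board would rely to see who is exposed to study procedures.

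**Working it through.** No calculation applies. The check sets the statements side by side and looks for one that makes consent a condition of placing a device.

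1. **Who may enter LOCK?** Anyone staff think will benefit, consented or not (Section 7(n); DSMP 1.3.a; Section 12).
2. **What does LOCK entry bring?** Actigraph and Fitbit assessment, without a consent qualifier (Section 8(a) item 5; DSMP 1.1).
3. **Are the devices ordinary care or research?** Section 3(b) makes them the primary research data collection. Section 7(n), Section 2 item 5, says all resident data in the study are collected by the home as standard clinical practice. Both cannot be right for actigraph and Fitbit data.
4. **Taking 1 to 3 together:** a resident without consent may be entered into LOCK and, by the risk text, then receives two research devices.
5. **Does another passage close the gap?**
   - *Data-sharing limit in the consent note:* it governs what reaches the researchers, not who wears a device.
   - *Consented-only data sources (Sections 3(b) and 10(c)):* these contradict step 4, since collecting actigraph data requires wearing the actigraph. They are the best evidence of intent, but they do not say that placement requires consent.
   - *Weekly list of consented residents with study numbers (item c of the resident data flow, DSMP 1.3.b and Section 10(c)):* its stated purpose is to let the home verify which identifiable data researchers may see. It is not tied to issuing devices.
   - *Subject numbers on devices (item e of the same lists):* these apply to devices mailed back. On the way out, Section 3(b), Study Staff Training, describes storage envelopes with a space for the resident's name.
   - *Right to refuse (Section 8(a) item 7, repeated in Sections 9(b) and 12):* it covers the devices but is framed as the refusal right that applies to usual care. It is an opt-out, not prior consent.
   - *Assent and distress rules (Section 7(n)):* these allow withdrawal once a device is in use. They do not supply consent beforehand.
6. **Result:** three statements allow LOCK entry without consent, two attach the devices to LOCK entry, two leave the meaning of enrolled open, and two limit device data to consented residents. None states that a device may be placed only on a consented resident.

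**The case against.** The strongest reply is that the risk text uses LOCK loosely to mean the study. Section 8(a) item 5 answers a form question about risks of study procedures and goes on to speak of a participant. DSMP 1.1 sits under a heading about participants. If LOCK contains only standard practice and the devices are research, the devices are by definition outside LOCK. Sections 3(b) and 10(c) limit collection, not merely sharing, to consented residents, and the data flow places the consented list before assessment. Device instruction within LOCK training does not settle who wears a device, because nursing home staff collect all the data and need that training in any case.

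Most of this stands as evidence of intent, and consented-only is the more plausible intention. It does not remove the conflict: the sentence about who receives devices names LOCK enrolment, and LOCK enrolment is expressly separated from consent.

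A reader might also infer that data from unconsented residents would leave the home, because completed devices are mailed weekly and downloaded at the university. The documents do not support that. The consent note bars sharing such data, and returned devices are identified by subject number. Nor do they support claims that recordings would have to be destroyed or that the link between device and resident is at risk; devices are for single-resident use.

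**Conclusion.** The contradiction is real and should be resolved. The consent sections allow LOCK entry regardless of consent, the risk section and DSMP attach the actigraph and Fitbit to LOCK entry, and Sections 3(b) and 10(c) limit device data to consented residents. Followed literally by staff with no researcher on site, the first two put research devices on cognitively impaired residents without consent.

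It is tempting to go further and call this a failure of participant protection, or to say that unconsented residents will wear devices. The documents do not show that: the consented-only data text, the weekly list and the assent and refusal rules all point to a narrower intent.

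The size cannot be expressed as a number of residents. The plan gives 70 consents but neither the number of residents with dementia in the three homes nor a consent rate, and staff are to focus LOCK on those with the greatest sleep problems, so unconsented residents cannot be equated with LOCK entrants. The conclusion needs no numerical assumption. It rests on reading the device sentence and the entry rule as written.

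**What to change.** - In Section 8(a) item 5 and DSMP 1.1, describe those who receive the devices as consented study residents instead of residents enrolled in LOCK.
- In the LOCK-entry note in Section 7(n), DSMP 1.3.a and Section 12, add that no actigraph or Fitbit is placed on a resident who is not on the weekly consented list.
- In item d of the resident data flow, in DSMP 1.3.b and Section 10(c), change enrolled to consented for those whose assessment data are collected.
- Reconcile Section 7(n), Section 2 item 5 (all resident data are standard practice) and Section 8(a) item 7 (devices refused as part of usual care, repeated in Sections 9(b) and 12) with Section 3(b), where the devices are primary research data collection.
- Assign each device to a subject number when it is issued, not only when it is returned, and say so in staff training.

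The cost is wording in the places named and a small change to how devices are labelled on issue. The measurement schedule, sample size and analysis are untouched.

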1.0 Participant Safety

1.1 Potential Risks and Benefits for Participants

Potential Risks

The risks for participants in this trial are minimal. There are no anticipated physical or economic risks associated with this study. Regarding psychological risks to NH residents, the LOCK sleep program including frontline huddling provides a sequence of steps for the process of assessing and responding to sleep problems. During the intervention period NH residents enrolled in the LOCK sleep program will receive actigraph and Fitbit assessment, and although our team's experience with use of these devices in hundreds of people with dementia indicates that they are widely tolerated as comfortable, there is a small risk a resident may find the devices to be uncomfortable or otherwise distressing. As part of their intervention training, staff will be instructed on

behavioral signs of distress. If a participant exhibits significant behavioral distress due to assessment, staff will be instructed on modifications and alternatives. If the distress does not subside, staff will be instructed to discontinue the assessment (staff training also discussed in 1.3.b. Protection Against Risks).

For both NH residents and staff, an unlikely legal or social risk associated with participating in this study would be invasion of privacy in the remote chance that there is a loss or lack of protection of data containing personally identifiable information. These are research risks, not therapeutic risks. The study team will use careful procedures to guard the security and confidentiality of all data (see 1.3.b. Protection Against Risks).

For both NH residents and staff, a potential risk is that a person may not want to participate in the study and may feel coerced to do so. Therefore, to minimize this type of risk, all informed consent contact with potential participants will come through the study staff only, and all NH staff participation discussions and decisions will be kept confidential (see 1.3.b. Protection Against Risks).

Potential Benefits

The intervention may benefit NH residents by leading to better and earlier detection and treatment of sleep problems and from increased attention to their conditions. The intervention may benefit NH staff by improving communication and teamwork, thereby improving the work experience.

1.2 Adverse Event/Serious Adverse Event/Unanticipated Problem Collection and Reporting

Definitions

We will follow OHRP and UA IRB guidance and policies regarding definitions, collection, and reporting of Adverse Events (AEs), Serious Adverse Events (SAEs), and Unanticipated Problems (UPs). We expect that there will potentially be four categories of events/problems as follows: 1) Anticipated AEs unrelated to the intervention, 2) Anticipated AEs related to the intervention, 3) Unanticipated AEs and unanticipated problems unrelated to the intervention, and 4) Unanticipated AEs and unanticipated problems related to the intervention.

Reporting

As per National Institute on Aging (NIA) policy, all deaths will be reported within 24 hours of the study staff's knowledge of death to the NIA Program Officer and the DSMB Chair. Unanticipated SAEs related to the intervention will be reported within 48 hours of the study staff's knowledge of death to the NIA Program Officer and the DSMB Chair. A summary of all other SAEs will be reported quarterly to the NIA Program Officer and the DSMB DSMB Chair.

Study staff will continue to follow up with the participant and their treating clinical team until any clinical events have resolved. If there is a SAE that is thought by a treating clinician, co-investigator nurse scientist [name], study consultant geriatrician [name], or [name] to be possibly or probably related to the intervention, the PI will immediately notify the DSMB and NIA Program Officer. The PI or designee will also immediately communicate with the NH leadership team and corporate coach at the NH for immediate investigation by the relevant treating team. Any insights about any possible iatrogenic effects of any components of the intervention will be immediately shared with all active NH intervention sites.

Grading Scale and Study Relatedness Criteria

Anticipated AEs unrelated to the intervention: NH residents enrolled in the trial will have dementia and likely will have other pre-existing significant health issues that require NH

placement. It is anticipated that some participants will experience health events (new conditions or worsening of previous conditions), hospitalization, or death during the trial that will be due to the dementia and/or other pre-existing significant health issues and unrelated to the intervention. As per NIA policy, all deaths will be reported to the NIA and IRB within 24 hours, regardless of relation to intervention.

Anticipated AEs related to the intervention: Intervention-related AEs for NH residents might include: a) actigraph/fitbit-related skin reactions such as redness, itching, or other skin conditions or discomfort; b) distress or discomfort associated with actigraph/fitbit-related wear or NH staff attention; c) distress or discomfort associated with other LOCK sleep intervention NH staff attention or requests. Intervention-related AEs for NH staff might include: distress related to interview questions. Such events may be reportable depending upon the seriousness of the event and increase of risk to participant. The NH's treating clinical team's opinion of the seriousness of the event will be solicited and the PI, co-investigator nurse scientist [name] and study co-investigator geriatrician [name] will be consulted to determine seriousness and reportability of the event.

Unanticipated AEs and unanticipated problems related to the intervention: As with intervention-related AEs, unanticipated AEs and unanticipated problems will be evaluated for seriousness with input from the NH's treating clinical team (if applicable), the PI and clinical study team members Drs. [name] and [name] (if applicable) or data-related study team members including data coordinating center leader and study statistician [name] (if applicable).

1.3 Protection Against Study Risks

a. Informed Consent and Assent

Study staff will obtain all necessary IRB authorizations for protocols and materials described below. All consents will be conducted by an IRB-approved study staff member who has been trained by [name]. The study staff member will be responsible for explaining the study, answering questions, and obtaining informed consent.

NH Resident Consent – Step 1. Legally Authorized Representative Consent NH leadership team or their designees will identify all NH residents with an ADRD diagnosis and mail to their legally authorized representatives (LARs) an IRB-approved study introduction letter (including option to opt out within one month if they do not wish to be contacted by study staff). Opt-out procedures have been demonstrated to yield higher response rates and lower rates of non-response bias compared to opt-in procedures, and to be acceptable to participants, with no difference in rates of reported distress or complaints compared to opt-in procedures.105-108 In our past federally funded research involving people with dementia, opt-out consent has been approved by multiple IRBs and worked well. Contact information of those LARs not opting out will be shared with University of Alabama (UA) study staff. We will request of the IRB a waiver of consent and HIPAA authorization for screening purposes regarding the sharing of these contact information.

Study staff will mail an IRB-approved study information packet via a tracked, express mailing service to all LARs who do not opt out. These materials will include a cover letter, an IRB-approved informed consent form (ICF), and an express mail return envelope so the LAR can send the signed ICF to the UA study office. LARs will be encouraged to contact study staff via phone or email for an appointment to discuss the study and go through the consent form together before signing the ICFs. Study staff will contact the LARs via phone and/or email within one week of sending the packet and will re-contact the LAR up to 6 times within the next month as needed to establish contact (if contact has not been established within one month, and NH staff are not able to determine that the LAR's contact information has changed, then the lack of contact will

be considered a soft refusal and no other contact will be attempted).

During a phone appointment, study staff will review all important elements of the ICF with the LAR, including the following: description of the study, information on how to contact the investigators and the NH administrator and director of nursing, a statement that there is no prejudice for refusal to participate, a statement that the subject may withdraw from the study at any time without prejudice, and statement regarding risk and benefit of participation. The LAR will be encouraged to ask questions. The LAR will be encouraged to call the PI if they have any remaining questions before signing the consent form.

NH Resident Consent – Step 2. Screening for Capacity for NH Resident Consent/NH Resident Assent

Some NH residents with mild ADRD may have the capacity to provide their own consent. FOR RESIDENTS WITH LIKELY MILD ADRD AND AN LAR WHO CAN BE CONTACTED, a CONSERVATIVE two-step process will be used to address the ethical balance of the beneficence of assuring that residents who do not have the capacity to consent are protected by LAR oversight with the promotion of autonomy for residents who do have capacity to consent. Once LAR consent is received for a resident, the NH leadership team will be asked to identify that resident's most recent MDS Brief Interview for Mental Status (BIMS) [reference #120], a cognitive screening measure with good reliability and validity. For residents with BIMS scores in the mild range (above 10), the NH leadership team will be asked to arrange and support a telephone appointment between that resident and a study staff person (if the resident turns out to not have the cognitive ability to participate in the following telephone-based procedure, then they would also not have the cognitive capacity to provide informed consent, which requires higher level cognitive abilities).

In the telephone appointment, the study staff member will provide information about the study and will screen for capacity to consent by assessing the following. Does the resident respond appropriately to a social greeting? Is the resident oriented to place? Does the resident understand who the study team member is after the team member explains their identity? During the course of this introductory conversation, was the resident able to respond fluently and socially appropriately? If so, the team member will go through the consent form with them. Residents will then be asked a series of questions to assure their understanding. These questions are as follows:

Describe in your own words what this study is about?

Describe what I am asking you to do to participate in this study?

Are you required to do this interview with me?

What will happen if you don't talk to me?

What happens if you decide you don't want to participate once we get started? What will I do with the information you give me?

The NH leadership team member will support this telephone conversation by assuring that the resident has a quiet environment to have the telephone conversation and that the resident has in front of them a printed large-font version of the ICF with the signature area flagged. If the resident is able to respond appropriately to all the capacity screening questions, and they do wish to participate, then the resident will be instructed to sign the ICF. The study staff person will contact the NH leadership team member and ask them to make a copy of the ICF for the resident to keep, place a copy in the medical chart, and express mail the original to the UA study office using a provided pre-paid envelope. If the resident is able to respond appropriately to all the capacity screening questions and does not wish to participate then they will not be enrolled in the study, regardless of the LAR's consent. In this case, the study team member will let the NH leadership team and the LAR know that the resident has declined participation.

Under all circumstances, the NH resident's autonomy will be respected. For NH residents without capacity to consent, their assent to participate will be obtained whenever possible, and their decision to withdraw at any time (whether expressed verbally or by resistance to participation) will be honored (see also staff training in 1.3.b. Protection Against Risks).

FOR RESIDENTS WITH LIKELY MILD ADRD (BIMS SCORE ABOVE 10) BUT NO LAR, THE NURSING HOME LEADERSHIP TEAM AND STUDY STAFF WILL GO DIRECTLY TO THE RESIDENT TO INVITE THEIR PARTICIPATION AND SCREEN THEIR CAPACITY TO CONSENT USING THE SAME PROCESS DESCRIBED ABOVE.

All above procedures apply to securing consent for the study team to have access to NH resident personally identifiable data. We note that because the LOCK sleep program does not include any activities that are outside of standard NH practice, NH staff will be free to enroll any NH residents that they believe will benefit into the LOCK sleep program regardless of resident consent status; but the NH leadership team will only share with researchers data from residents who are consented for the study.

NH Staff Consent

The NH leadership team or their designees will provide to all NH staff an IRB-approved study introduction letter (including option to opt out within two weeks if they do not wish to be contacted by study staff). Contact information of those NH staff not opting out will be shared with UA study staff. We will request of the IRB a waiver of consent for screening purposes regarding the sharing of these contact information.

UA Study staff will contact NH staff (via email and/or phone, see next paragraph) to invite them to participate in mid-implementation phone interviews. Study staff will also contact NH staff to invite them to participate in post-implementation interviews (phone). The list of NH staff who agree and decline interview participation will remain confidential to protect NH staff from any possible coercion to participate (see 1.3.b. Protection Against Risks).

For mid-implementation interviews, study team members will, on the PI's behalf, send out e-mails to all NH staff who do not opt out. The first e-mail will contain text from [name] soliciting voluntary participation in the telephone interviews. E-mail reminders will be sent, one in each of the four weeks after the initial e-mail, with follow up phone calls to the participant's work phone to remind them about the email. All emails will include information on how to opt out of the study. We will continue recruitment until we have recruited the desired sample size or until one month has passed. To facilitate staff involvement, we will secure permission from the director of each NH that staff may take part in the study during their normal hours of work. For post-implementation interviews, study team members will follow these same procedures. In addition, a study team member will virtually visit each NH in person at the end of the intervention period to work with NH staff to collect information from the enrolled NH residents' medical record and also to recruit for and conduct any needed remaining post-implementation phone interviews. The study staff person will virtually attend change of shift meetings, huddles, and other staff meetings to invite interview participation and will also invite staff to contact research staff for virtual one-on-one discussions if staff member has questions about volunteering to participate. We have successfully used similar procedures in our previous federally funded studies involving NH staff.

In all recruitment activities, it will be made clear that participation is strictly voluntary and no adverse consequences to the person's job status or any other adverse consequences will occur if the person declines to participate in these activities and that their final decision to participate or not will be kept confidential from all NH and

corporate staff.

Mid-implementation interviews will take place via telephone or teleconference platform. Post-implementation interviews will take place via telephone or teleconference platform.

We will apply for a waiver of documentation of informed consent for the 1-hour, audiorecorded mid-implementation and post-implementation interviews, allowing us to obtain verbal consent. We will provide a consent information sheet to potential participants in the stead of an informed consent document that requires signature. We will record each subject giving permission to be recorded on the audio recording.

The study staff member will review with the NH staff member all relevant elements of consent on the consent information sheet, including the following: description of the study activities, time requirement, information on how to contact the investigators, a statement that there is no prejudice for refusal to participate, a statement that the subject may withdraw from the study at any time without prejudice, a statement encouraging the reader to ask questions, and a statement regarding risk and benefit of participation. All informed consent guidelines of the IRB will be followed. If at any time during the interview the staff member indicates a desire to stop participating, the participant will be withdrawn from the interview portion of the study. Confidentiality of all interview data will be protected by using participant code numbers on the data collection forms.

b. Protection Against Risks

Study staff training

To protect all vulnerable subjects, in addition to the NIH-required computer-based trainings (on the protection of human research participants, HIPAA, and Good Clinical Practice), the UA study staff will attend a 2-day training session specific to the proposed project led by [name]. The PI will review the overall goals of the study, study policies and procedures, data collection manuals, adverse event identification and reporting, subject confidentiality, communication techniques and principles for working with persons with dementia, and appropriate procedures for working by telephone with LARs for consent, for working by telephone with people with dementia for consent and for determining capacity to consent. Procedures will be reviewed for protecting employees from possible coercion for participation from supervisors including maintaining confidentiality of those employees who do and do not consent to research interviews. During these training sessions, professionally produced videotapes of staff interactions with persons with dementia will be shown and the PI and study staff will role play all informed consent, capacity assessment, and data collection processes. [name] will provide training on appropriate assessment equipment maintenance and data downloading. Drs. [name] and [name] will provide training on appropriate procedures for NH staff interviews.

NH leadership team training: The NH leadership team will complete NIH-required computer-based trainings (on the protection of human research participants, HIPAA, and Good Clinical Principles). Study staff will also provide a 2-hour training on procedures to protect vulnerable subjects, as follows: proper procedure for, and importance of only using IRB-approved procedures and letters when sending study opt-out letters to LARs; proper procedures for maintaining security and privacy of data packages mailed to the University of Alabama project office; proper procedures for avoiding coercion or appearance of coercion of research participation when working with NH staff (e.g., not asking staff about research interview participation); proper procedures for assisting in telephone appointment arrangements and providing logistical support when study team members conduct telephone-based NH resident consenting and capacity to consent assessment; importance of only study team members conducting actual consent procedures of anyone (LARs, NH residents, NH staff);

importance of only properly trained NH leadership team members participating in study procedures. [name] (via zoom teleconference) will work together to provide training on the appropriate application of actigraphs and Fitbits to promote comfort and prevent adverse experiences, as well as appropriate assessment equipment maintenance and data mailing.

NH staff training: As part of the intervention training, NH staff will be trained by their NH leadership teams or their trained designees on proper use and placement of actigraphs and Fitbits, verbal and behavioral signs of distress that might indicate actigraph/Fitbit-related discomfort/distress, and appropriate modification techniques to try to relieve such distress. NH staff will be informed that the devices should be removed in the unlikely event that distress behaviors are not relieved by modification techniques. NH staff will be trained on importance of NH resident autonomy, and will be engaged in a discussion of how to assess for and honor NH resident assent or lack thereof with regard to the devices.

